[name]., Ph.D. (Co-Principal Investigator) University of Washington, Department of Psychiatry & Behavioral Sciences, [name]
[contact]

[name] (Co-Investigator), University of Southern California, [name],
[contact]

[name], MPH, .(Co-Investigator), Division of General Internal Medicine and Geriatrics, Institute for Healthcare Studies, Feinberg School of Medicine, Northwestern University, [name], [contact]

[name], MPH, FACP (Co-Investigator), Division of General Internal Medicine and Geriatrics, Institute for Healthcare Studies, Feinberg School of Medicine, Northwestern University, [name], [contact]

[name], MPP (Co-Investigator), BlueCross BlueShield of Massachusetts, Boston, MA 02116,
[contact]

[name] (Co-Investigator), UCLA Anderson School of Management, [name], [contact]

[name]. (Co-Investigator), UCLA Anderson School of Management, [name], [contact]

[name]. (Project Manager) Leonard D. Schaeffer Center for Health Policy and Economics, University of Southern California, [name], Office: [contact], [contact], [contact]

PARTICIPATING STUDY SITES

Northwestern University. [name]., M.P.H., FACP and [name]., M.P.H., Division of General Internal Medicine and Geriatrics, Institute for Healthcare Studies, Feinberg School of Medicine, Northwestern University, [name], [contact] [contact]

PRÉCIS

Study Title

Application of Economics & Social psychology to improve Opioid Prescribing Safety (AESOPS): R21 pilot

Objectives

There is a lack of evidence that long-term opioid use offers benefit for noncancer pain and an abundance of evidence of harm. The objective of the Application of Economics & Social psychology to improve Opioid Prescribing Safety (AESOPS) study is to develop and test novel behavioral nudges to encourage adherence to Oregon Pain Guidance and CDC guidelines for opioid prescribing for persons with noncancer pain. Once we have successfully developed different nudges in the R21 phase, we will then compare these nudge interventions in a future cluster randomized trial.

Design and Outcomes

The purpose of this pilot project is to test EHR behavioral interventions to encourage safer opioid prescribing during ambulatory visits when pain is a symptom. Changes in opioid prescribing among primary care clinicians will be measured for three types of patients:

1): **Opioid naïve**: Visit where the order is for an included opioid and there is no prior opioid prescription with a start date of greater than 1 day and less than 91 days, 2) **At-risk for long term use**: Visit where the order is for an included opioid there is a prior opioid prescription with a start date greater than 1 day and less than 91 days, and there is no prior opioid prescription with a start date greater than 90 days, and 3) **Long-term opioid recipient**: Total opioid doses are at least 50 MME per day, there are two or more prior opioid prescriptions with two different start dates both greater than 1 day and less than 91 days, and there is a prior opioid prescription with a start date greater than 90 days and less than 181 days.

Outcome Measure: The primary outcome is average weekly morphine milligram equivalents (MME) prescribed per-clinician.

1. **STUDY OBJECTIVES**

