1.1 Primary Objective

The objective of the R21 pilot phase of the Application of Economics & Social psychology to improve Opioid Prescribing Safety (AESOPS) study is to develop and test novel behavioral nudges to encourage adherence to pain and CDC guidelines for opioid prescribing for persons with noncancer pain. At the time of opioid prescribing, clinicians will be prompted with an EHR nudge when the prescribing history for the patient falls into one of the following three mutually exclusive categories: Opioid naïve, At-risk for long term use, or Long-term opioid recipient. The primary outcome is average weekly morphine milligram equivalents (MME) prescribed per-clinician.

2. **BACKGROUND AND RATIONALE**

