2.1 Background on Condition, Disease, or Other Primary Study Focus

Over the last two decades, prescription opioids have grown to become a public health crisis. Today, on average 1 in 5 persons with chronic noncancer pain receives an opioid prescription in the U.S.¹ Yet, despite this record level of prescribing, reports of pain in America have not gone down.^{10,11} The greater availability of prescription opioids has been accompanied by alarming rise in the negative consequences related to their use. In 2015, there were over 365,000 emergency department visits for misuse and 20,101 prescription overdose deaths, more than have ever been recorded in U.S. history.⁵ The costs of prescription opioids are staggering. Aggregate costs for prescription opioid harms are estimated at over \$78.5 billion (in 2013 dollars). One-fourth of the aggregate economic burden is publicly funded (i.e., Medicaid, Medicare, and veterans' programs).^{12,13}

In 2016, the CDC issued the “CDC Guideline for Prescribing Opioids for Chronic Pain” which gives 12 patient care recommendations: (1) *use alternatives to opioids*, (2) *set realistic goals* for pain and function, (3) *discuss opioid risks* upon therapy initiation, (4) *use immediate release agents* instead of long-acting ones, (5) *use lowest effective starting dose, avoid escalation* above 50 milligram (mg) morphine equivalent (ME) daily dose and abide by a 90 mg ME/day dose prescribing limit, (6) *prescribe lowest dose at lowest quantity needed for acute pain*—usually 3 days with a maximum of 7 days in rare cases, (7) *evaluate for and discuss tapering* within 1 - 4 weeks and after 90 days, (8) *prescribe naloxone and evaluate substance use history* with opioid prescription, (9) *review the state prescription drug monitoring program data* (10) *conduct urine drug tests* to provide information about drug use that is not reported by the patient, (11) *avoid co-prescribing* with benzodiazepines, and (12) *refer patients with opioid use disorder to medication-assisted treatment in combination with behavioral therapies*. Our objective is to increase adherence to the CDC guideline and Oregon Pain Guidance pain management guideline. To evaluate the effects of doing so, we will measure as a primary outcomes clinician aggregate monthly mg ME

for patient visits with ≥ 50 mg ME daily dose. Secondary outcome is rate of dose escalation to ≥ 50 mg ME/day.

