5.2 Handling of Study Interventions

The following interventions will be tested: *Accountable Justification (AJ)* is an EHR-based intervention that will prompt the clinician to justify, in a free text response, the decision to prescribe an opioid or to not reduce high risk/high dose prescribing. The prompt is designed to inform the clinician that the justification will be seen by others in the patient's medical record as an "High risk prescribing justification" note, and that if no justification is entered, the phrase "no justification given" will appear in the note.

Delivery of AJ nudges in Epic's electronic health record (EHR) based on patient type is described below.

Opioid-naïve: An automated search of EHR data determines whether the patient received an opioid prescription within 90 days. If no opioid was prescribed, the clinician receives an alert cautioning against initiating a prescription based on current guidelines. The clinician can either remove or continue with the current opioid prescription. The former results in return to normal workflow after receiving a prompt recommending physical therapy and non-opioid alternatives. The latter, however, induces a prompt requiring the clinician to justify their decision in free text. A Justification Note with the clinician's response is recorded in the Visit Summary portion of the patient's record. A generic "No justification given" is generated for blank responses.

At-risk for long term use: If an automated search of EHR data reveals an opioid prescription(s) within 90 days of the current order, but no previous opioid prescription prior to 90 days before, a prompt explaining the danger of continuing refills based on current guidelines appears. The process is otherwise the same as above; clinicians who cancel a prescription receive a prompt recommending non-opioid alternatives and physical therapy, whereas those who continue with the order are required to justify their decision.

Long term opioid recipient: If an automated search of EHR data reveals total opioid doses are at least 50 MME per day, there are two or more prior opioid prescriptions with two different start dates both greater than 1 day and less than 91 days, and there is a prior opioid prescription with a start date greater than 90 days and less than 181 days, a prompt suggesting an opioid taper appears.

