9.5 Data Analyses

For sample descriptive statistics, we will use means and medians for continuous measures, frequencies for count data, and standard deviations and interquartile ranges for variance. For inferential analysis, our primary hypothesis is that milligram morphine equivalent dose will decrease for persons on high doses of opioid therapy.

10. Statistical Analysis

Measures

The primary outcome is average weekly morphine milligram equivalents (MME) prescribed per-clinician. We assessed change in average per-clinician weekly MME from the 34-week baseline period before, to the 34-week period post-intervention using a mixed-effects, knotted spline, left censored regression to account for baseline differences in prescribing, a non-linear change in the rate of opioid prescribing from baseline to post-intervention, and an inflated number of weeks with an average MME of zero, respectively. Predictors include the fixed effects time in weeks, time with a knot at the intervention start, and a random intercept for clinician. The density function to achieve maximum likelihood estimates for a left censored regression is the observed probability of y_i assuming normal distribution ($x_i\beta, \sigma^2$) given that $y_i > 0$, weighted by the probability that y_i is above a censoring threshold, in this case zero.² Because uncensored observations are often skewed, we used log average weekly MME as our dependent variable. The percentage change in log MME per one unit increase in the uncensored, or latent variable was

measured using:

$$\log(MME)^* = \beta_0 + \beta_1 Time + \beta_2 (Time - t^*) + \zeta + error^1$$

where $\log(MME)^*$ is the latent, uncensored variable, time is the number of weeks, t^* is the spline knot for the intervention start, and ζ is the clinician random effect.¹ We adjusted the coefficients by calculating the average partial effect to interpret not just the linear change in $\log(MME^*)$, but the non-linear likelihood that $\log(MME^*)$ is uncensored, resulting in comparable estimates to ordinary least squares.²

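### By-type and high-dose results would select on the dose the nudge aims to lower, because no rule fixes long-term membership before the intervention; the all-patient primary outcome is not affected

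*Combined protocol and SAP*

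**What the plan says.** The Précis (Design and Outcomes) announces by-type measurement: "Changes in opioid prescribing among primary care clinicians will be measured for three types of patients". The same three definitions appear there and in Section 9.1.

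The long-term type has a dose condition, "Total opioid doses are at least 50 MME per day", and a history condition: two or more prescriptions started within the last 90 days, and "there is a prior opioid prescription with a start date greater than 90 days and less than 181 days". The at-risk type requires that "there is no prior opioid prescription with a start date greater than 90 days". The naïve type requires no prescription in the 90-day window.

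Section 1.1 describes when a patient is assigned to a category: "At the time of opioid prescribing, clinicians will be prompted with an EHR nudge when the prescribing history for the patient falls into one". Under Section 5.2, when the long-term conditions are met, "a prompt suggesting an opioid taper appears".

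Two other places concern high-dose prescribing:
- Section 2.1 gives a primary outcome of aggregate monthly dose per clinician, "for patient visits with ≥ 50 mg ME daily dose".
- Section 9.5 says that "our primary hypothesis is that milligram morphine equivalent dose will decrease for persons on high doses of opioid therapy".

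The primary outcome in the Précis and Sections 1.1, 3 and 10 is average weekly MME per clinician; Sections 9.1 and 9.4.1 also use weekly MME per clinician. The Section 10 model has time in weeks, a knot at the intervention start and a clinician random intercept. It has no patient-type term. The visit criteria in Section 4.1 contain no type or dose condition.

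**The concern.** For the long-term type, one membership condition is the quantity the nudge is meant to reduce. If type is re-assessed at each order, a successful taper can remove the patient from the group in which the change is measured. No section fixes membership at a date before the intervention, so the only definition available to an analyst is the one written for the alert.

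The by-type result and the result for persons on high doses are at stake. The Section 10 model has no type term, so it cannot by itself answer the Section 9.5 hypothesis. Some subgroup analysis is needed, and its answer would depend on who is still in the group. The pilot is meant to lead to a cluster randomized trial, so a distorted high-dose result could be carried forward.

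**Working it through.** The documents state no effect size, power or dose distribution, so there is no planned figure to reproduce. All doses below are assumptions.

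**Step 1: where a tapered patient goes.** Take a patient with three prescriptions started in days 2–90 and three in days 91–180.
- At 60 MME/day, all long-term conditions are met.
- At 45 or 49 MME/day, the dose condition fails. The patient is not naïve (prescriptions within 90 days) and not at-risk (a prescription older than 90 days).

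The patient therefore belongs to no type, and the remaining dose drops out of all by-type measurement.

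**Step 2: direction.** Dropping doses below 50 from a post-period sum can only lower the sum. Dropping them from a post-period mean can only raise the mean. Exits alone therefore make a within-type total overstate the fall and a within-type mean understate it.

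**Step 3: small examples.**
- Four patients at 50, 60, 90 and 120: total 320, mean 80. A 10% taper gives 45, 54, 81 and 108, total 288, a true change of −10%. Re-selecting at 50 or more keeps 54 + 81 + 108 = 243. The total changes by 243/320 − 1 = −24%, and the mean goes from 80 to 81 (+1%).
- The same four with a 20% taper: 72 + 96 = 168 remain. The total changes by 168/320 − 1 = −47.5%, and the mean goes from 80 to 84 (+5%).
- One patient going from 60 to 45 and one staying at 100: the true total change is 145/160 − 1 = −9.4%. Within the type, the total changes by 100/160 − 1 = −37.5% and the mean by 100/80 − 1 = +25%.

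**Step 4: exponential excess, 10% taper.** Let dose = 50 + E, with E exponential of mean m. A patient stays if 0.9 × dose ≥ 50, that is E ≥ 5.56.
- Share staying = exp(−5.56/m).
- Mean ratio = (50 + 0.9m)/(50 + m).
- Total ratio = share staying × mean ratio.

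| m | Share staying | Change in mean | Change in total | True change |
|---|---|---|---|---|
| 20 | 0.757 | 68/70 − 1 = −2.9% | −26% | −10% |
| 40 | 0.870 | 86/90 − 1 = −4.4% | −17% | −10% |
| 60 | 0.912 | 104/110 − 1 = −5.5% | −14% | −10% |

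**Step 5: a second assumed shape.** Doses are lognormal (log-SD 0.6), with a 20% taper in patients at 50 or more. This is a simulation of 400,000 doses per scenario, without the history conditions.

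| Median dose | Cohort fixed at baseline | Total, re-selected | Mean, re-selected | All-patient total | Leaving the group |
|---|---|---|---|---|---|
| 40 | −20.0% | −39.9% | −6.7% | −11.8% | 35.6% |
| 60 | −20.0% | −31.2% | −9.8% | −16.3% | 23.7% |
| 90 | −20.0% | −24.8% | −13.7% | −18.9% | 12.9% |

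The fixed cohort recovers the 20% taper exactly. The all-patient total equals the actual change in prescribed MME, because no tapered patient is dropped. It is smaller than 20% only because untapered patients are included.

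**The case against.** The strongest reply is that the analysed outcome is untouched. A reader might infer from the type definition that the trial's primary result is wrong. The documents do not support that: a patient tapered from 60 to 48 still contributes the remaining dose to weekly MME per clinician, and neither the model nor the visit criteria refer to type or dose. This part of the reply stands in full.

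Four further points limit the concern:
- Re-assessment at the order is documented for delivering the alert, where using dose at that time is not a statistical fault. The documents do not say whether the 50 MME/day total includes the new order or which dates it covers. If it rests on earlier orders only, the first tapered order would still count in the type; exit would be delayed rather than prevented.
- No by-type total, mean or model is written, and Section 9.4.2 lists no secondary outcomes. The bias would arise if the alert definition were used for analysis; it is not a fault in a specified model.
- A reader might conclude that the Section 9.5 hypothesis cannot be answered. That goes too far. The sentence does not cite the 50 MME cut or the long-term type, and it is open to a fixed-cohort reading.
- The sizes rest on assumed doses. The mean rises only in the small hand-chosen examples; in every exponential and lognormal scenario with a taper it still falls, but by too little.

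These points narrow the scope. They do not supply a membership rule for a measurement that the Précis announces.

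**Conclusion.** The concern holds for the by-type change in the Précis, for the Section 2.1 outcome restricted to visits at 50 or more, and for the Section 9.5 hypothesis if the same cut is re-applied at each order. It does not hold for all-patient average weekly MME per clinician.

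For the affected results the direction is known and opposite for the two natural summaries. The size is not known. The 10% and 20% illustrations show that it could be comparable to the effect itself: with a mean excess of 20 MME, a true 10% fall would appear as 26% in the total and 2.9% in the mean. These figures assume a uniform taper, exits only, and immediate re-classification on the tapered dose.

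Section 2.1 raises a separate conflict. It names a monthly primary outcome restricted by dose, while the other sections use weekly MME per clinician without that restriction. The sections need to be reconciled.

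**What to change.** For analysis only, leaving the alert trigger unchanged:

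1. For by-type and high-dose results, assign long-term membership from orders dated before the start of each 34-week period, using the Précis definition with the period start as the reference date. State which orders and dates make up the daily total.
2. Keep those patients in the group for the whole period, and count all their later MME, including orders below 50 MME/day and zero.
3. Form the baseline cohort by the identical lookback before the baseline period, so that regression to the mean after selection on a high dose is handled alike in both periods.
4. State that the all-patient weekly MME outcome is not restricted by type.
5. Reconcile Section 2.1 with the Précis and Sections 1.1, 3, 9.1, 9.4.1, 9.5 and 10 on the primary outcome and its population.

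Assigning membership at the first qualifying order inside each period would not be enough. In the intervention period that order comes after nudges begin. In the four-patient example, if the 10% taper is made at the first prompted order and that order sets the dose, the patient at 50 is ordered 45 and never enters. The total is again 320 to 243.

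The cost is SAP wording and programming, plus order data from before baseline. The definition reaches back 180 days. The intervention cohort's lookback fits inside the 34-week baseline period (34 × 7 = 238 days), so only the baseline cohort needs earlier records. The main downside is that patients who first become long-term during a period are left out of the type-specific result. They remain in the all-patient outcome.

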1.1 Primary Objective

The objective of the R21 pilot phase of the Application of Economics & Social psychology to improve Opioid Prescribing Safety (AESOPS) study is to develop and test novel behavioral nudges to encourage adherence to pain and CDC guidelines for opioid prescribing for persons with noncancer pain. At the time of opioid prescribing, clinicians will be prompted with an EHR nudge when the prescribing history for the patient falls into one of the following three mutually exclusive categories: Opioid naïve, At-risk for long term use, or Long-term opioid recipient. The primary outcome is average weekly morphine milligram equivalents (MME) prescribed per-clinician.

2. **BACKGROUND AND RATIONALE**

2.1 Background on Condition, Disease, or Other Primary Study Focus

Over the last two decades, prescription opioids have grown to become a public health crisis. Today, on average 1 in 5 persons with chronic noncancer pain receives an opioid prescription in the U.S.¹ Yet, despite this record level of prescribing, reports of pain in America have not gone down.^{10,11} The greater availability of prescription opioids has been accompanied by alarming rise in the negative consequences related to their use. In 2015, there were over 365,000 emergency department visits for misuse and 20,101 prescription overdose deaths, more than have ever been recorded in U.S. history.⁵ The costs of prescription opioids are staggering. Aggregate costs for prescription opioid harms are estimated at over \$78.5 billion (in 2013 dollars). One-fourth of the aggregate economic burden is publicly funded (i.e., Medicaid, Medicare, and veterans' programs).^{12,13}

In 2016, the CDC issued the “CDC Guideline for Prescribing Opioids for Chronic Pain” which gives 12 patient care recommendations: (1) *use alternatives to opioids*, (2) *set realistic goals* for pain and function, (3) *discuss opioid risks* upon therapy initiation, (4) *use immediate release agents* instead of long-acting ones, (5) *use lowest effective starting dose, avoid escalation* above 50 milligram (mg) morphine equivalent (ME) daily dose and abide by a 90 mg ME/day dose prescribing limit, (6) *prescribe lowest dose at lowest quantity needed for acute pain*—usually 3 days with a maximum of 7 days in rare cases, (7) *evaluate for and discuss tapering* within 1 - 4 weeks and after 90 days, (8) *prescribe naloxone and evaluate substance use history* with opioid prescription, (9) *review the state prescription drug monitoring program data* (10) *conduct urine drug tests* to provide information about drug use that is not reported by the patient, (11) *avoid co-prescribing* with benzodiazepines, and (12) *refer patients with opioid use disorder to medication-assisted treatment in combination with behavioral therapies*. Our objective is to increase adherence to the CDC guideline and Oregon Pain Guidance pain management guideline. To evaluate the effects of doing so, we will measure as a primary outcomes clinician aggregate monthly mg ME

for patient visits with ≥ 50 mg ME daily dose. Secondary outcome is rate of dose escalation to ≥ 50 mg ME/day.

2.2 Study Rationale

Rationale for Accountable Justifications. In the Accountable Justifications intervention, clinicians will be prompted to record an explicit justification for why they are prescribing an opioid that appears in the patient's EHR. Accountable justifications incorporate several behavioral principles. First, they signal an injunctive norm (a norm, often provided by an authoritative source, that strongly indicates how people should behave) indicating that prescribing an opioid is not recommended. This may make the clinician more likely to believe both that not prescribing an opioid is the best medical decision and that prescribing when it is not indicated violates professional standards. Second, it incorporates social accountability. A clinician justification become an explicit, separate part of the medical record, so a clinician's decision to prescribe is subject to the review and judgment of the provider's peers. Third, the justification alert implicitly designates guideline-concordant prescribing as the default action. Defaults are options that are exercised if the decision maker takes no special action to opt in or out of a given choice. Prior to our intervention, choosing to deviate from guidelines did not carry a special requirement to document a clinical rationale in the EHR. Accountable justifications, therefore, reset the default action. Guideline-concordant treatment choices will not require special justification, but a clinician must now "opt-in" to prescribing an opioid by providing a justification for which they are accountable.

